8.3 STUDY FLOW AND EXPECTED DURATION OF PATIENT PARTICIPATION

All patients will participate in a Screening Phase, Treatment Phase, and Follow-up Phase.

Screening Phase:

- A 14-day screening period before enrollment (\leq 28 days for baseline biopsy and imaging)
- Patients will be evaluated against study inclusion and exclusion criteria. Patients must meet all inclusion criteria and none of the exclusion criteria at screening in order to be eligible for the study. Assessments required on C1D1 that are performed as part of the screening evaluations and within 72 hours prior to the first dose of study treatment, do not need to be repeated on C1D1.

Treatment Phase:

- Arm A: mRNA-2416 administered for 6 cycles
- Arm B: Combination dosing of mRNA-2416 with durvalumab for 6 cycles. Following completion of 6 cycles of combination dosing, patients may continue with durvalumab as a single-agent until disease progression, unacceptable toxicity, or 24 months of treatment (total), whichever is sooner.

Safety Follow-up:

- Patients will be followed up for safety evaluation 30 and 90 days after their last dose of study treatment.

Disease Progression Follow-up:

Patients who complete study treatment with an overall tumor assessment of stable disease (SD) or better will be followed for tumor assessment 60 and 180 days after their last dose of study treatment, or until disease progression, whichever occurs first.

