10.5 Dose Omissions and Discontinuation of Study Drug Administration

Study treatment may be interrupted for situations other than treatment-related AEs such as medical and/or surgical events or logistical reasons not related to study treatment. Patients should be placed back on study

treatment within 3 weeks of the scheduled interruption, unless otherwise discussed with the Sponsor. The reason for interruption should be documented in the patient's study record.

Patients who have permanently discontinued study therapy will be scheduled for an End of Treatment visit within 14 days (± 2 days) of the decision to permanently discontinue study therapy and assessments will be performed per the Schedule of Events table ([Section 3](#)). Patients who have permanently discontinued study therapy should not be considered withdrawn from the study. They should return for the 30-day and 90-day safety follow-up visit from last dose and the tumor assessment follow-up visits per the Schedule of Events table. If the patient fails to return for these assessments for unknown reasons, every effort (e.g. telephone, email, letter) should be made to contact them.

The following are reasons for discontinuing study therapy without necessarily requiring withdrawal from the study:

- Patients who have completed 6 cycles of study therapy and have an overall tumor assessment of SD or better
- Patients who have experienced a Grade 4 treatment-related AE at any time during study treatment must discontinue from study treatment
- Patients who, in the opinion of the investigator, have incurred a Grade 3 drug-related DLT that has not recovered to Grade 1 or less within 14 days, or has recurred following restarting study therapy at a modified dose level.
- Patients who, in the opinion of the investigator, have incurred unacceptable toxicity that does not meet the pre-determined criteria for DLT (eg, late-onset, treatment-emergent toxicity after the DLT assessment window, or Grade 2 toxicities that are sufficiently durable or unresponsive to supportive intervention as to render them unacceptable in the opinion of the investigator) which has not recovered to Grade 1 or less within 28 days, or has recurred following restarting study therapy at a modified dose level.
- Patients who experience a Grade 3 hypersensitivity reaction or autoimmune events must discontinue from study treatment
- Patients who no longer have lesions that meet criteria for injection
- Pregnancy
- Physician's decision

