- Patient/guardian decision
- Patients will be withdrawn from study due to progressive disease per irRC/LYRIC. Due to the possibility of pseudoprogression; patients should not be withdrawn from the study due to progressive disease per RECIST v1.1 or Cheson 2014 criteria.
- Patient has received alternative anti-cancer therapy
- Patient has symptomatic progression of disease, or other clinical conditions which, in the opinion of the investigator, render it in the interests of the patient to withdraw from the study.

The reason for discontinuation of study therapy should be recorded on the appropriate page(s) of the electronic case report form (eCRF).

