10.6 DISCONTINUATION FROM THE STUDY

Patients will be permanently discontinued from the study following completion of the EOT, 30-day and 90-day safety follow-up visits. Additional reasons for discontinuation from the study include the following:

- Patient withdraws consent
- Unwillingness to comply with study requirements

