 - Subject is tolerating study drug

All decisions to continue treatment beyond disease progression must be discussed with the Sponsor/Medical Monitor and documented in the study records. Disease progression will be confirmed after at least 4 weeks per irRC/LYRIC. If disease progression is confirmed per irRC/LYRIC, the patient will discontinue study therapy. The local investigator's assessment will be used for the analysis of response according to both RECIST 1.1 and irRC/Lyric, and for treatment decision making (study discontinuation due to PD as per irRC). Patients experiencing progressive disease per RECIST v. 1.1 criteria may continue to be treated according to irRC guidelines until progression is documented via irRC. Imaging data may be centrally collected and checked for quality by an imaging Contract Research Organization (CRO) designated by Moderna. The local investigator's assessment will be used for the data analysis and for treatment decision making. Central review of the imaging data may be performed if deemed necessary.

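### Protocol 10.5 and one phrase in 10.10 take patients off study at immune-related progression, against 8.3, 10.6 and the rest of 10.5, which keep them in safety follow-up to day 90

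*Protocol*

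**What the plan says.** Two places tie immune-related progression to leaving the study. A bullet in protocol 10.5 reads "Patients will be withdrawn from study due to progressive disease per irRC/LYRIC". In 10.10, the sentence on the use of the local investigator's assessment refers to "treatment decision making (study discontinuation due to PD as per irRC" (the closing bracket follows). A later bullet in 10.5, on symptomatic progression, also speaks of withdrawing from the study.

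The other passages separate stopping therapy from leaving the study:

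- The list that holds both bullets is introduced with "The following are reasons for discontinuing study therapy without necessarily requiring withdrawal from the study".
- The paragraph before that list says "Patients who have permanently discontinued study therapy should not be considered withdrawn from the study", and then "They should return for the 30-day and 90-day safety follow-up visit from last dose".
- Protocol 8.3: "Patients will be followed up for safety evaluation 30 and 90 days after their last dose of study treatment".
- Protocol 10.6: "Patients will be permanently discontinued from the study following completion of the EOT, 30-day and 90-day safety follow-up visits". The only additional reasons it gives are withdrawal of consent and unwillingness to comply.
- Elsewhere in 10.10: "If disease progression is confirmed per irRC/LYRIC, the patient will discontinue study therapy".
- SAP 5.1 lists disease progression among the reasons for stopping each drug. Its reasons for leaving follow-up are withdrawal of consent, alternate anti-cancer therapy, death, loss to follow-up and other.

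**The concern.** A site reading the irRC/LYRIC bullet on its own would close the patient's participation at progression. A site reading 8.3 or the start of 10.5 would bring the same patient back at 30 and 90 days. The two sites would then observe adverse events over different lengths of time after the last dose.

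This matters because the incidence, nature and severity of AEs and SAEs is a Phase I primary endpoint (protocol 7.2). SAP 9.1 takes AE percentages out of all patients in the safety set and specifies no adjustment for time observed. A patient whose follow-up is cut short stays in the denominator, while any later event is missing from the numerator. Protocol 8.4.3 also uses DLT-type events after day 28 when the recommended dose for expansion is chosen, so late events have a use beyond description. Progression has no category of its own among the SAP's follow-up exit reasons, so such exits would probably be recorded as other and be hard to see in the disposition table.

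**Working it through.** The plan gives no figure to reproduce. The check is a comparison of passages, followed by arithmetic on the visit windows.

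**Step 1. What each place implies at irRC/LYRIC progression.**

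| Place | Therapy | Study status | 30- and 90-day safety visits |
|---|---|---|---|
| 10.5, irRC/LYRIC bullet | stops | ends | not provided for |
| 10.10, parenthesis | stops | ends | not provided for |
| 10.5, text before the list | stops | continues | required |
| 10.5, list introduction | stops | need not end | silent |
| 10.10, sentence on confirmed progression | stops | silent | silent |
| 8.3, safety follow-up | – | continues | required, no exception |
| 10.6 | – | ends after the visits | required first |
| SAP 5.1 | progression is a category | progression is not a category | – |

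The rows agree on therapy and disagree on study status. The list introduction does not settle it: it says withdrawal is not necessarily required, which leaves room for an item that does require it, and the bullet is worded as definite.

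**Step 2. Which visits can be lost.** The Schedule of Events gives the safety visits a window of -2/+7 days.

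- 30-day visit: 30 − 2 = day 28 to 30 + 7 = day 37.
- 90-day visit: 90 − 2 = day 88 to 90 + 7 = day 97.

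Let d be the number of days from last dose to withdrawal.

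- d below 28: both visits are lost.
- d from 28 to 87: the 30-day visit can have been made; the 90-day visit is lost.
- d of 88 or more: both can have been made.

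The value of d is not fixed by the protocol. Injections are every 2 weeks in Arm A superficial lesions, and every 4 weeks after Cycle 1 in Arm B and in visceral lesions. Scans are every 56 days, and irRC progression is confirmed at least 4 weeks after it is first seen. Taking d = 14, 28 and 56 as illustrations: at 14 both visits are lost; at 28 the 30-day visit can be done that day; at 56 its window has passed. The 90-day visit is lost in all three, so it is the surer loss.

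**Step 3. The AE reporting period.** Protocol 12.1.1 and 12.2 end it at the last safety visit or at study discontinuation, taking the later of the two. If the visits are made, the period runs to the 90-day visit. If a patient is withdrawn at d between 28 and 87 and makes no later visit, both dates fall before day 88, and so does the later of them. The qualifier protects the window only when the visits take place.

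**Step 4. Exposure, Arm B only.** Protocol 6.5 gives a durvalumab half-life of about 21 days. Assuming first-order decline, the fraction of the level at last dose is 2^(−30/21) = 0.37 at day 30 and 2^(−90/21) = 0.05 at day 90. The interval most likely to be lost is therefore one in which durvalumab is still clearing. This is context only and says nothing about Arm A, which receives no durvalumab.

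**Step 5. How many patients.** Disease progression is one of 11 categories in the SAP's list of reasons for stopping mRNA-2416. No expected or observed frequency is given, so no count can be derived.

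**The case against.** The strongest reply is that the governing text is clear. The opening of 10.5, section 8.3, section 10.6 and the Schedule of Events all keep the patient in safety follow-up. The list containing the bullet concerns stopping therapy and ends by asking for the reason therapy was stopped. Section 12.2 restricts AE collection to treatment-related events once a new antineoplastic therapy starts, which presupposes collection after treatment ends. On this view the bullet is loose wording and no site would act on it. Much of this stands: the weight of the text is on one side, and nothing in the documents shows a site applying the bullet literally. It does not remove the conflict, because a definite instruction in the protocol gives such a site textual support, and 10.10 uses the same language.

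Stronger readings are tempting, and the documents do not support them. A reader might infer that progression is the commonest reason for stopping and put a patient count on the problem; no frequency is given. A reader might assign a fixed number of lost follow-up days; that depends on dosing interval, scan timing and confirmation. A reader might say that AE reporting simply stops at withdrawal; that leaves out the later-of-two-dates qualifier. Delayed immune-mediated events are also not named separately as a primary endpoint; the endpoint is AEs and SAEs.

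**Conclusion.** The inconsistency is real and in current text: one bullet in 10.5 and one parenthesis in 10.10 end study participation at irRC/LYRIC progression, while the opening of 10.5, 8.3, 10.6, the other sentence in 10.10 and SAP 5.1 do not. For a patient handled under the bullet, the loss is the 90-day visit whenever withdrawal falls before day 88 after the last dose, and both visits when it falls before day 28. AE and SAE collection could then be uneven between sites, with later events undercounted where the bullet is applied. That effect is conditional on literal application, and its size across the trial is unknown. The text conflict is certain; the consequence is possible rather than shown. It merits correction because the affected data serve a primary endpoint and the remedy is small.

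**What to change.** Reconcile the irRC/LYRIC bullet and the symptomatic-progression bullet in 10.5, and the parenthesis in 10.10, with 8.3, 10.6 and the opening of 10.5. The wording should separate study status from study therapy, and make plain that the EOT, 30-day and 90-day safety visits already required apply to patients who stop for progression.

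The sentence in 10.5 on RECIST/Cheson progression needs separate care. It sits in a list about stopping therapy but speaks of withdrawal from the study, while 10.10 permits treatment beyond such progression only under stated conditions and after discussion with the sponsor or medical monitor. The two should be reconciled without creating a new rule on when treatment stops; which clinical rule applies is for the sponsor to state.

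The cost is wording in an amendment, with the usual IRB approval. The visits are already in the Schedule of Events. Site payment terms are in the Clinical Trial Agreement, which is not among the documents. If the text can no longer be changed, a SAP table of 30- and 90-day visit completion by reason for stopping would show whether the conflict affected the data.

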10.6 DISCONTINUATION FROM THE STUDY

Patients will be permanently discontinued from the study following completion of the EOT, 30-day and 90-day safety follow-up visits. Additional reasons for discontinuation from the study include the following:

- Patient withdraws consent
- Unwillingness to comply with study requirements

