	
• Arm A: mRNA-2416 alone• Arm B: mRNA-2416 in combination with durvalumab (PD-L1 inhibitor) 
Each arm of the study consists of a Dose Escalation and Dose Confirmation part followed by a Dose Expansion part in ovarian cancer. Each dose level in the Dose Escalation period will be conducted using a standard 3+3 study design in order to determine the safety and tolerability of each dose. For Arm A Dose Escalation, once a dose level has been cleared for safety, that dose level is open to enrollment of up to 9 additional patients who are willing and eligible to undergo tumor biopsy. Once the expected MTD/RDE has been cleared in Dose Escalation for Arm A, Dose Escalation in Arm B will begin with mRNA-2416 at 1 dose level lower than the Arm A MTD/RDE according to Table 1.
 
For both Arms, once the expected MTD/RDE has been cleared in Dose Escalation, Dose Confirmation of the MTD/RDE will be conducted in at least 3 patients with visceral lesions injectable with ultrasound or CT guidance. Dose Confirmation will be conducted in the same fashion as Dose Escalation, as described in Section 8.2.1 and Section 8.4.
 
For both Arms, once the MTD and/or RDE has been determined in Dose Escalation/Confirmation, patients will be enrolled in an Expansion cohort in order to assess the preliminary anti-tumor activity of mRNA-2416 in ovarian cancer of epithelial origin
 
The Dose Expansion will consist of 2 investigational groups across the treatment arms summarized as follows and shown in Figure 1:
 
Arm A: mRNA-2416 alone
 
• Group 1: Ovarian cancer 
Arm B: mRNA-2416 in combination with durvalumab
 
• Group 2: Ovarian cancer 
Prior to enrollment, all patients will undergo screening to determine study eligibility. All patients completing study therapy with an overall tumor assessment of stable disease (SD) or better will be followed for 6 months or until disease progression, whichever occurs first.

Study Duration	Approximately 3.5 years

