3 SCHEDULE OF EVENTS

Study Procedure	Screening	Cycle 1				Cycle 2 - Cycle 6		End of Treatment	Follow-up	
Study Days	-14 to -1	1	2	8	15	1	15	Within 14 days of Treatment Discontinuation	30 and 90 Day Safety F/U	90 and 180 Day Disease Progression F/U Period
Visit Window	-	-	+1 day		±2 days	±2 days		±2 days	-2/+7 days	±30 days
Clinical Assessments										
Informed Consent	X									
Inclusion/exclusion criteria	X									
Demographics ¹	X									
Medical/Surgical/Cancer Histories ²	X									
Vital Signs ³	X	X	X	X	X	X	X	X	X	
Height	X									
Body Weight	X	X				X		X	X	
Physical Exam ⁴	X							X		
Symptom-directed Physical Exam		X	X	X	X	X	X		X	
ECOG Performance Status	X					X		X	X	
Concomitant Medications ⁵	X	X	X	X	X	X	X	X	X	
Adverse Events	X	X	X	X	X	X	X	X	X	X
Clinical Laboratory Assessments										
Full Blood Count ⁶	X	X	X	X	X	X	X	X	X	
Coagulation ⁶	X	X				X				
Serum Chemistry Panel ⁶	X	X	X	X	X	X	X	X	X	
Thyroid Function ¹²	X	X			X	X		X	X	
Urinalysis ⁶	X							X		
Pregnancy Test ¹⁰	X	X				X		X	X	
12-Lead Electrocardiogram	X							X	X	
HIV, Hepatitis B & C Tests ^{6,11}	X									
Study Drug Administration										

Study Procedure	Screening	Cycle 1				Cycle 2 - Cycle 6		End of Treatment	Follow-up	
Study Days	-14 to -1	1	2	8	15	1	15	Within 14 days of Treatment Discontinuation	30 and 90 Day Safety F/U	90 and 180 Day Disease Progression F/U Period
Visit Window	-	-	+1 day	±2 days		±2 days	±2 days	-2/+7 days	±30 days	
mRNA-2416 intratumoral injection ⁷		X			X	X	X ⁷			
Durvalumab infusion		X				X				
Tumor Assessments										
Tumor assessment ⁸	X					C3 & C5		X		X
PK/Pharmacodynamic Assessments										
PK Sampling ⁹		X	X	X		C2				
Cytokine Profile Sampling ⁹		X	X	X		C2				
Serum Immunogenicity Sample ⁹		X			X	X	C3 & C6	X		
Tumor Biopsy	X	Refer to Section 10.5								

1. Demographics include age, sex, race, and ethnicity.
2. Prior cancer history includes (i) date of diagnosis, (ii) staging, (iii) all previous therapies (ie, chemotherapy, immunotherapy, biologic or targeted agents, experimental therapies, radiotherapy, and surgery), (iv) previous therapy details (ie, regimen, start and stop dates), and (v) best response for each regimen.
3. Vital signs include temperature, blood pressure, preferably in seated position, and pulse rate. Pre-dose and as clinically indicated before every infusion or administration.

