10.10 RADIOLOGIC ASSESSMENTS

For the purpose of this clinical trial, the following imaging will be acquired at Screening for a baseline tumor assessment and on study:

- CT (with contrast) or magnetic resonance imaging (MRI) of the chest, abdomen and pelvis
- CT (with contrast) or MRI of the neck, if clinically indicated
- Bone scan if clinically indicated

- PET-CT (for lymphoma)

All patients will have tumor assessments performed within 28 days prior to C1D1, every 56 days from C1D1 (\pm 7 days), and during Disease Progression Follow-up Period at 90 and 180 days following the end of treatment (\pm 30 days).

At screening, all patients will undergo CT with IV contrast of the chest, abdomen and pelvis. MRI should only be used to evaluate sites of disease that are not adequately imaged by CT. If a patient is intolerant of iodine-based contrast agents, CTs may be performed without contrast. MRI may be used to evaluate sites of disease where a CT without IV contrast is not adequate. Visible skin lesions and easily palpable subcutaneous tumors may be measured by physical examination using a ruler or calipers. Bone scans should be performed within past 60 days prior to Cycle 1 Day 1. If the baseline bone scan is positive, scans should be repeated at Cycle 3 Day 1, Cycle 5 Day 1, at the end of Cycle 6, and during Disease Progression Follow-up Period at 90 and 180 days following the end of treatment (\pm 30 days).

For optimal evaluation of patients, the same methods of assessment and technique should be used to characterize each identified and reported lesion at baseline and during follow-up. Target lesions should be selected and measured as per RECIST guidelines (see [Appendix C](#) and [Appendix D](#)).

At the investigator's discretion, imaging studies may be repeated at any time if disease progression is suspected. Due to the possibility of pseudoprogression, patients will be permitted to continue with treatment beyond initial RECIST 1.1 or Cheson defined disease progression as long as they meet the following criteria:

- If, in the opinion of the investigator, he/she is continuing to receive clinical benefit as defined by:
 - Absence of clinical symptoms and signs (including worsening of laboratory values) indicating disease progression
 - No decline in ECOG performance status
 - Absence of rapid progression of disease or of progressive tumor at critical anatomical sites (e.g., cord compression) requiring urgent alternative medical intervention.

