3.1. Overall Study Design and Plan

This is an open-label, multicenter, Phase I/II Dose Escalation study of repeated intratumoral injections of mRNA-2416 alone (Arm A) and in combination with intravenously administered durvalumab (Arm B) in patients with advanced relapsed/refractory solid tumor malignancies or lymphoma, followed by Expansion period in patients with ovarian cancer in each treatment arm. Each arm of the study consists of a Dose Escalation Period in non-visceral lesions and a Dose Confirmation period in visceral lesions followed by a Dose Expansion Period in ovarian cancer.

Each dose level in the Dose Escalation Period will be conducted using a standard 3+3 study design in order to determine the safety and tolerability of each dose. For Arm A Dose Escalation, once a dose level has been cleared for safety, that dose level is open to enrollment of up to 9 additional patients who are willing and eligible to undergo tumor biopsy.

Once the expected MTD/RDE has been cleared in Dose Escalation for Arm A, Dose Escalation in Arm B will begin with mRNA-2416 at 1 dose level lower than the Arm A MTD/RDE according to the protocol Table 1.

For both arms, once the expected MTD/RDE has been cleared in Dose Escalation, Dose Confirmation of the MTD/RDE will be conducted in at least 3 patients with ovarian cancer with visceral lesions injectable

with ultrasound or computer tomography (CT) guidance. Dose Confirmation will be conducted in the same fashion as Dose Escalation.

For both arms, once the MTD and/or RDE has been determined in Dose Escalation/Confirmation, patients will be enrolled in the Expansion cohort in order to assess the preliminary anti-tumor activity of mRNA-2416 in ovarian cancer of epithelial origin.

Prior to enrollment, all patients will undergo screening to determine study eligibility. Arm A patients will receive mRNA-2416 for 6 cycles with 28 days in each cycle. Arm B patients will receive mRNA-2416 in combination with durvalumab for 6 cycles with 28 days in each cycle. Following completion of 6 cycles of combination dosing, patients may continue with durvalumab as a single-agent until disease progression, unacceptable toxicity, or 24 months of treatment (total), whichever is sooner. Patients completing study therapy with an overall tumor assessment of stable disease (SD) or better will be followed for efficacy for 6 months or until disease progression, whichever occurs first. Schedule of events can be found in the protocol.

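### Protocol 10.6 ends study participation at the 90-day safety visit while other sections carry tumor follow-up to 180 days, and the sections also disagree on the first follow-up scan, its anchor date and who is followed

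*Protocol*

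**What the plan says.** **When participation ends.** Protocol 10.6: "Patients will be permanently discontinued from the study following completion of the EOT, 30-day and 90-day safety follow-up visits". Section 8.3 dates those safety visits from the last dose: "Patients will be followed up for safety evaluation 30 and 90 days after their last dose of study treatment". The Schedule of Events gives them a window of -2/+7 days.

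**How long tumor follow-up lasts.** The Schedule has a column headed "90 and 180 Day Disease Progression F/U Period", with a window of ±30 days. Section 10.10 has scans "during Disease Progression Follow-up Period at 90 and 180 days following the end of treatment", also ±30 days. Under Section 8.3, patients "will be followed for tumor assessment 60 and 180 days after their last dose of study treatment". The synopsis says they "will be followed for 6 months or until disease progression, whichever occurs first", and SAP 3.1 says they "will be followed for efficacy for 6 months or until disease progression, whichever occurs first".

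**Who is followed.** Protocol 8.3, the synopsis and SAP 3.1 restrict tumor follow-up to patients who complete treatment with stable disease or better. Protocol 10.5 covers everyone who permanently stops study therapy. It says they are not to be treated as withdrawn and should return for the tumor visits in the Schedule.

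**How the endpoints use this.** SAP 3.2.2 lists PFS and DOR as secondary endpoints. SAP 8.2 and 8.3 observe them up to the last date of study participation (or data cutoff or, for DOR, death) and censor event-free patients at the last adequate scan showing stable disease or better.

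**The concern.** Section 10.6 is where the protocol defines leaving the study, and as written it puts that point before the last planned tumor assessment. A site following it would never do the 180-day scan. A site following 10.5 and the Schedule would.

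Because the SAP bounds PFS and DOR by the last date of study participation, the exit rule feeds directly into censoring. At stake are the late part of the PFS curve and the duration of lasting responses, with observation time that could differ between sites for reasons unrelated to the patients. The 60- versus 90-day conflict and the two anchors add a smaller problem: progression dates depend on scan dates, and sites can time the first off-treatment scan differently.

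**Working it through.** The documents state no figure for this point: no sample size, power or event count rests on PFS, DOR or follow-up length. The check is therefore calendar arithmetic on the stated visits, followed by a sensitivity calculation under assumptions of mine.

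**1. Exit against the 180-day scan.** Inputs: six 28-day cycles; last injection on Cycle 6 Day 15 (Arm A, superficial lesions) or Cycle 6 Day 1 (visceral lesions, or Arm B stopping after Cycle 6); safety visit at 90 days (-2/+7); scan at 180 days (±30). Day 1 is the first dose and all visits are counted from the last dose.

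| | Arm A superficial | Visceral, or Arm B stopping after Cycle 6 |
|---|---|---|
| Last dose | 5×28 + 15 = Day 155 | 5×28 + 1 = Day 141 |
| Exit under 10.6 (+90) | Day 245 (243–252) | Day 231 (229–238) |
| 180-day scan | Day 335 (305–365) | Day 321 (291–351) |
| Nominal loss | 335 − 245 = 90 days | 321 − 231 = 90 days |
| Share of span to the 180-day scan | 90/335 = 27% | 90/321 = 28% |

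The windows do not rescue the scan. Its earliest date is 180 − 30 = 150 days after last dose, and the latest safety visit is at 90 + 7 = 97 days.

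**2. The 90-day scan.** Its window is 90 ± 30, or days 60 to 120. A scan on days 98 to 120 falls after the latest possible exit, so it can be lost too.

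**3. 60 against 90 days.** Section 8.3 gives no window for its 60-day scan. On a common anchor, day 60 is exactly the lower edge of 90 ± 30, so one scan could just satisfy both. Any end-of-treatment date later than the last dose breaks this. If end of treatment is taken as Day 169 (assumption: the day after six full cycles), the 10.10 window is Days 229–289. The 8.3 scan for an Arm A superficial patient is at 155 + 60 = Day 215, outside it.

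**4. How many patients could be affected.** Assume exponential PFS with median m months, S(t) = exp(−ln 2 × t / (30.4375 × m)), and that every patient still progression-free completes six cycles and is followed. The medians are my assumptions. The share progressing in the lost interval is S(245) − S(335). Counts are for 27 evaluable patients in Arm A and, using Days 231 and 321, 41 in Arm B.

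| Median (months) | Progression-free at Day 169 | Progress Day 245–335 | Of 27 | Of 41 |
|---|---|---|---|---|
| 2 | 14.6% | 3.9% | 1.1 | 1.9 |
| 3 | 27.7% | 7.7% | 2.1 | 3.5 |
| 4 | 38.2% | 9.9% | 2.7 | 4.4 |
| 6 | 52.7% | 11.4% | 3.1 | 4.9 |
| 9 | 65.2% | 11.0% | 3.0 | 4.7 |

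The Arm B counts assume nobody continues durvalumab after Cycle 6.

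**5. Effect on the median.** Day 169 is 169/30.4375 ≈ 5.5 months. A median below that is reached on treatment, so the Kaplan-Meier median would hardly change. The loss falls on the tail and on DOR in late or lasting responders.

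**The case against.** The strongest reply is that 10.6 stands alone. Section 10.5, directly before it, says patients off therapy are not withdrawn and sends them back for the tumor visits. The Schedule, 8.3, 10.10, the synopsis and SAP 3.1 all plan 180 days or 6 months, and SAP 5.1 reports end of study by completion of the follow-up period. On that reading, sites would do the 180-day scan and nothing is lost.

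This stands as a limit on the claim. A reader might infer that PFS and DOR are in fact truncated; the documents do not support that, only that they would be if 10.6 is applied as written. But 10.5 does not amend 10.6. Adjacent sections give incompatible instructions, and 10.5 does not settle the scan day or anchor in 8.3.

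Three other stronger readings also fail:

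- A reader might set 8.3 against 10.10 on who is followed, since 10.10 speaks of all patients. Section 10.10 can be read as giving timing only, for patients who enter the follow-up period. The clear contrast is between 8.3 and 10.5.
- A reader might give the 60-day scan a ±30-day window. The documents attach that window only to the 90- and 180-day visits.
- A reader might take 90 days as the most that can be lost. It is the nominal loss, not a bound, because a late 90-day scan can be lost too.

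It is also fair to say that PFS and DOR are descriptive here, and that Arm B patients may stay on durvalumab for up to 24 months in total, which moves their last dose and all follow-up dates later.

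**Conclusion.** The inconsistency is real and more than clerical, because the exit date enters the SAP's censoring rules. Its effect is conditional and moderate. Under a literal 10.6, the 180-day scan falls after exit whatever the windows, and the 90-day scan can as well.

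Under exponential PFS with assumed medians of 2 to 9 months, about 4% to 11% of patients would progress in the nominal lost interval: roughly 1 to 3 of 27 in Arm A and 2 to 5 of 41 in Arm B, fewer in Arm B if durvalumab continues. Only patients progression-free after stopping treatment are affected.

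The primary response-rate test and the sample size do not rest on follow-up length. The point should be corrected, but it does not threaten the main conclusion of either arm.

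**What to change.** Amend Protocol 10.6 so that patients without progression leave the study only after the final (180-day) tumor assessment or progression, whichever comes first, in line with the other sections. Then reconcile Protocol 8.3, 10.5 and 10.10, the Schedule of Events, the synopsis and SAP 3.1 to:

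- one follow-up scan schedule, with its window;
- one anchor date, either last dose or end of treatment;
- one follow-up population, either patients completing treatment with stable disease or better or all who stop therapy.

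The last date of study participation in SAP 8.2 and 8.3 then has a single meaning. The cost is wording only: the 180-day scan is already in the Schedule, so the 10.6 change adds no assessment.
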